8.6.2.2 At ELISA/PRNT testing laboratory

- Samples are separated into 4 aliquots (ELISA, PRNT, repeat tests and archiving) SOP HPA 4/1
- Serum samples will be held at minus 20°C until ELISA or PRNT testing is undertaken

8.6.2.3 Storage of reserve aliquots of serum at testing laboratory in Pune

• Reserve aliquots of serum will be held at minus 20°C until required or for a minimum of 5 years post-licensure, as required by Indian regulations (See SOP HPA 4/1 for storage after testing).

8.6.2.4 Transportation of samples

- Whole blood samples will be transported from sampling sites to the initial processing site (SSH) by designated trial staff at 2-8°C (in vaccine carriers).
- Further transportation will be undertaken by a designated laboratory technician from Vadu Rural Hospital and will comply with Indian regulations. Serum samples will be held at minus 20°C during transportation.

8.6.3 Sample processing

8.6.3.1 Laboratory measurement of immunogenicity

- All serum samples will be tested by Enzygnost Anti-measles-virus/IgG ELISA (Dade-Behring, Marburg, Germany) (SOP HPA 5/1 and SOP HPA 6/1).
- In addition, all specimens with Enzygnost optical density readings <0.1 will be tested by plaque reduction neutralization test (SOP HPA 7/1).

8.6.4 Sample archiving

Unused portions of serum samples will be held at minus 20°C until a minimum of 5 years post licensure. Samples will be catalogued to allow rapid relocation as required.

8.7 Measurement of safety outcomes

Clinical events following vaccination will be investigated under the categories of: immediate adverse events (IAE); serious adverse events SAE, or other adverse events.

- Data on adverse events will be collected by Medical Officers at clinic visits (Days 0, 14, 28, 91 and, for infants in the Vadu area, day 364), and field workers at home visits (Days 3, 7, 10, 17, 21, 28, 56 and 182, 252 for subset of infants).
- Any adverse event detected during home visits that are graded moderate or severe (see Section 8.7.5, Visit 3 and Visit 6) or are unexpected will be immediately reported to the On-Call Medical Officer, who will examine the child, report the AE and treat, or refer for treatment, as required.

• At the end of each day, all CRFs with data about adverse events will be checked by a Study Medical Officer to ensure that all adverse events that are graded moderate or severe have been followed up, and that reports appear consistent.

8.7.1 Definitions

Acute clinical reactogenicity

Acute reactogenicity includes the expected reactions to vaccination occurring during the first 14 days post vaccination, reported at home visits, or clinic visits.

Adverse event (AE)

Any untoward medical occurrence in a patient or clinical investigation subject administered a pharmaceutical product which does not necessarily have a causal relationship with this treatment. An adverse event (AE) can therefore be any unfavourable and unintended sign (including an abnormal laboratory finding), symptom, or disease temporally associated with the use of a medicinal (investigation) product, whether or not related to the medicinal (investigation) product.⁴³ This definition includes all SAE and IAE.

Anaphylaxis

Exaggerated acute allergic reaction, occurring within 2 hours after immunization.⁴⁴ Anaphylaxis is a clinical syndrome characterized by sudden onset AND rapid progression of signs and symptoms AND involving 2 or more organ systems.⁴⁵

Immediate Adverse Events (IAE)

Any adverse event, serious or otherwise, occurring within 30 minutes of vaccine administration. This definition includes SAE occurring in this time period.

Serious adverse event (SAE)

Any adverse event that, at any dose, has one or more of the following attributes:^{43 46}

- 1. Results in death.
- 2. Is life-threatening.
- 3. Requires inpatient hospitalization or prolongation of existing hospitalization.
- 4. Results in persistent or significant disability/incapacity.
- 5. Results in an important medical event that may not be immediately life-threatening or does not directly result in death or hospitalization, but which may jeopardize the patient.

Unexpected adverse drug reaction

An adverse reaction, the nature or severity of which is not consistent with the applicable product information (e.g. that listed in the investigator's brochure). ^{42, 46, 43, 47}

8.7.2 Adverse event detection, management and reporting

Information about adverse events will be collected through a combination of: structured questionnaires administered at study clinic visits or home visits; active surveillance for events requiring medical treatment or hospitalization, or deaths; and reports from parents/guardians, who will be told by fieldworkers to report any medical conditions immediately on the Study Emergency Number and to seek treatment at SSH or KEM Hospital as appropriate.

The management of patients with adverse events and reporting procedure are described in detail in SOPs WHO 1/1, WHO 2/1 and WHO 3/1. In brief, the investigator/institution will ensure that adequate medical care is provided to a subject for any adverse event. At enrolment, parents/guardians will be given numbers to contact in the case of emergency and informed of other means of seeking medical treatment if they have no immediate access to a telephone. They will also be informed of how to seek medical treatment from either study staff or their local PHC for less urgent conditions. Contact has been made with PHCs regarding their participation in the treatment of study participants who attend PHCs and the reporting of these AE to the research team. SSH is currently the central referral hospital for the study area and in addition oversees PHCs in the Vadu region. Onward referrals from SSH will be to KEM Hospital (which administers SSH). The trial co-investigator at KEM will receive referrals from trial medical officers and ensure that prompt treatment is given. The co-investigator will also ensure mechanisms are in place so that any treatment of a subject in KEM Hospital which does not arrive via the referral method is promptly reported to him. He will monitor clinical care of any trial participant for the duration of their stay at KEM.

The principal investigator is responsible for ensuring that all serious adverse events are reported immediately by telephone or fax to the DSMB and the sponsor, as described in SOP WHO 3/1.

Participants will be reimbursed for expenses incurred in connection with their participation in research. During the period of research if the participant requires treatment for complaints other than those being studied, necessary free aneillary care or appropriate referrals will be provided.⁴⁸ The parents/guardians will be informed about the investigations regarding the event.

8.7.2.1 Immediate Adverse Events

See SOP VAD 4/1 (vaccination day)

Pulse rate, respiratory rate, blood pressure and axillary temperature will be measured prior to vaccination and during the 30 minute direct observation period. These will be recorded in the CRF.

Symptoms and signs of immediate reactions, treatments given and outcomes will be recorded and reported, as described in SOP VAD 4/1. Any serious events will be managed and reported as described in SOP WHO 2/1.

8.7.2.2 Additional adverse events

All non-serious adverse events will be assessed using structured questionnaires, either at clinic or home visits. The timing of these visits is described in section 8.5 and SOP VAD 5/1

The choice of specifically solicited adverse events is based on:

- Events observed in the phase 1 MAP trials in India;
- Additional adverse events seen in previous studies of aerosolized measles vaccine;
- Adverse events known to be associated with subcutaneous measles vaccination;
- Adverse events observed in trials of other vaccines administered by the respiratory route.

Detailed list of solicited adverse events and specific grading structure for each event type on a 4 level scale from 0 (none) to 3 (severe) are described in Appendix 3

Atypical measles syndrome

8.7.3 Adverse event reporting procedure

- All adverse events occurring during the trial should be accurately reported in case report form (SOPs WHO 1/1, WHO 2/1, WHO 3/1).
- Adverse events graded as **severe** will be reported by the PI to the WHO focal point within 24h of first knowledge by the Principal Investigator or any trial staff. The DSMB will be informed of these by the WHO focal point within 24 hours.
- The Principal Investigator will report all SAE immediately (within 24h of first knowledge by the principal investigator or any trial staff) to the WHO Focal Point and local ethical committees; even if the adverse event is considered not to be related to the investigation product. Notification will be made by fax and/or by telephone or email communication.
- The Principal Investigator should send promptly, within five working days, the serious adverse event report by fax, email or express mail to the WHO Focal Point.
- Any relevant information concerning the SAE that becomes available after the SAE report has been sent (outcome, precise description of medical history, results of the investigation, copy of hospitalization report, etc.) will be forwarded by the Principle Investigator as soon as possible to the WHO Focal Point.
- For reports of deaths, the investigator should provide WHO Focal Point with any additional requested information, e.g. autopsy reports and terminal medical reports. The anonymity of the subjects shall be respected when forwarding all information
- The WHO Focal Point will comply with the Indian regulatory requirements regarding SAE. The National Regulatory Authorities, WHO ethical committee, DSMB and Clinical Trial Monitor will be notified (e.g. by telephone, facsimile transmission, or in writing) by the WHO focal point as soon as possible (ideally within 24 hours) but no later than 7 calendar days after first knowledge by the WHO focal point that a case qualifies as an SAE, followed by as complete a report as possible within 8 additional calendar days. See SOP WHO 3/1.

8.7.4 Follow-up of Adverse Events and Serious Adverse Events

All AE will be followed up until the participant has reached one of the endpoints as described here.

- An adverse event that is likely to be related to the product and that persists at the end of the trial, or any SAE occurring after termination of the trial and likely to be related to the product, will be followed up by the investigators until the participant has completely recovered, recovered with sequelae, or died.
- All other AE will be followed up until the participant has completely recovered, or they complete the study.

A thorough investigation will be conducted to determine causality. Adverse events will be recorded in detail during the course of the trial, irrespective of the possible causal relationship with the measles vaccine.

8.7.5 Grading of adverse events

Adverse events will be graded using a specific grading structure for each event type on a 4 level scale from 0 (none) to 3 (severe). These are described in Appendix 3

8.7.6 Classification of association of events with vaccination

The investigator will assess whether any adverse event is related to the immunization using the following scale and according to the following definitions (based on Workbook for Investigators, WHO/TDR).

- Not related: The event is clearly related to other factors such as the patient's clinical state, therapeutic intervention or concomitant therapy.
- Unlikely to be related: The event was most probably produced by other factors such as the patient's clinical state, therapeutic intervention or concomitant therapy, and does not follow a known response pattern to the study vaccine.
- **Possibly related:** The event follows a reasonable temporal sequence from the time of study vaccine administration and/or follows a known pattern to the study vaccine but could have been produced by other factors such as the patient's clinical state, therapeutic intervention or concomitant therapy.
- **Probably related:** The event follows a reasonable temporal sequence from the time of study vaccine administration and/or follows a known response pattern to the study vaccine and could not have been produced by other factors such as the patient's clinical state, therapeutic intervention or concomitant therapy. These events include but are not limited to those that require medical attention and result in withdrawal from follow-up. Any available medical records needed to accurately describe the event will be obtained from the appropriate health care provider.
- **Most probably related:** The event follows a reasonable temporal sequence from the time of vaccine administration; and/or follows a known response pattern to the trial vaccine; and could not have been produced by other factors such as the patient's clinical state, therapeutic intervention or concomitant therapy; and either occurs immediately following trial vaccine administration, or there is positive reaction at the application site.
- **Insufficient data to assess:** There is not enough clinical and/or laboratory information to suggest the relationship between the experience and the trial product.

A report on all **Severe** Adverse Events and all **Serious** adverse events will be submitted to the DSMB within 7 days, following the Terms of Reference of the DSMB for the Measles Aerosol Project (Appendix 2). The DSMB will make the final decision on the classification of serious and severe adverse events.

In addition, the DSMB will receive summary reports of all AE quarterly (see DSMB TORs).

8.8 Measles surveillance in the study area

A surveillance system is to be established (as an entity separate from the trial) in the entire blocks containing the trial areas. It will be established as described in the WHO Best practices for measles surveillance⁴⁹ and in the Field Guide -Measles Surveillance & Outbreak

Investigation Guidelines⁵⁰ (2005) Government of India, Department of Family Welfare New Delhi.

It is expected that this surveillance system will be operational before the start date of the trial.

The primary purpose of measles surveillance will be to detect, in a timely manner, all areas in the trial whether the measles virus is circulating. Surveillance will be undertaken with support from the Immunization Programme of the State of Maharashtra and with the National Polio Surveillance Project in India. The surveillance system will involve the following:

- All the health facilities/health providers in the study area will be trained to implement timely notification of clinically diagnosed measles (probable) cases will be promoted to detect cases and outbreaks. A designated surveillance medical officer (SMO) will conduct monthly active searches in the registry files (outpatient and inpatient records) to ensure all probable measles cases are reported. All measles outbreaks will be serologically confirmed to differentiate them from other fever and rash outbreaks. The surveillance data should be analysed at all levels to determine and improve the immunization strategies.
- In addition, **during the home and clinic visits** the field workers, medical doctors and nurses will solicit information on the presence of cases of rash and fever illness in the household and in the neighbourhood where the infants enrolled in the trial reside. Any probable case will be reported to the designated SMO for it investigation as per the Field Guide -Measles Surveillance & Outbreak Investigation Guidelines.

Every confirmed case of measles (i.e. laboratory or epidemiological confirmation) and any confirmed outbreak in the study area or surrounding areas will be reported within 24 hours to the Principal Investigator by the State of Maharashtra EPI Manager and by the designated SMO. All confirmed measles cases will be managed according to the National guidelines including the administration of Vitamin A.

The designated SMO at each district will collect the surveillance forms (VPD - H002) from all the reporting units, collate them in designated format (VPD - D001 form) and compile the district report. The District Immunization Officer (DIO) will send this routinely every week to the State EPI officer, RC or State SMO by Tuesday of each week. The VPD-D002 form should be used to track completeness and timeliness of reporting from the reporting units. This information should be sent on a quarterly basis by the DIO to the State Programme Officer.

Moreover, the State of Maharashtra will share with the PI investigator monthly updates on the performance of the surveillance systems using the indicators defined in the Field Guide - Measles Surveillance & Outbreak Investigation Guidelines.

The DIO/SMO will analyse the available district/block data on a weekly basis, using and reconciling case information from different surveillance systems to identify outbreaks of measles. As per national guidelines, the presence of measles outbreak should be verified if five or more than five clinically diagnosed cases of measles are identified in a block in a week, or five or more than five confirmed cases of measles occur in an area bordering several blocks in a week, or one or more than one death due to measles occurs in a block in a week.

If possible outbreaks are identified, measles outbreak investigations should be initiated as described in Chapter 5, Measles Outbreak Investigation of the Field Guide -Measles Surveillance & Outbreak Investigation Guidelines. In brief, the DIO and the SMO will oversee that the following actions will take place:

- Identifying the measles outbreaks that need to be investigated and assigning an outbreak number
- Mobilization of Epidemic Response Team (ERT)
- Orientation & planning meeting at the local level
- Conducting measles case search
- Collection and shipment of specimens to the laboratory
- Laboratory confirmation of the outbreak
- Data analysis
- Conversion of data to information for action
- Report writing
- Giving feedback
- Initiating actions including vaccination activities.

8.9 Procedure for monitoring subject compliance

Each subject will be given an appointment card for the next schedule visit to the clinic. If any subjects do not turn up on the scheduled date, the investigator will send the designated field worker to their houses and request them to come to the clinic.

9 Assessment of Immunogenicity

9.1 Primary outcome

Measles seropositivity at day 91 post-vaccination.

Measles seropositive specimens are:

• specimens tested by Enzygnost Anti-measles-virus/IgG (Dade-Behring, Marburg, Germany) enzyme-linked immunosorbent assay with optical density signal \geq 0.1, or

specimens tested by Enzygnost with optical density signal < 0.1, that are subsequently tested by plaque reduction neutralization test with a result of $\ge 120 \text{ mIU/ml}$ measles antibody titre.

For further details, please see Sample processing (HPA 1/1, WHO 2/1, WHO 3/1, WHO 4/1), Measurement of outcomes (SOP HPA 5/1, HPA 6/1, HPA 7/1)

9.2 Secondary outcomes

For all infants:

- Geometric mean titres, pre-vaccination and at day 91;
- Seroconversion (defined as a change from Enzygost OD <0.1 to OD \ge 0.1 or PRNT from <120 to \ge 120 mIU/mL) measured in paired samples from day 0 and day 91;
- As covariates for inclusion in multivariable analyses: age; sex; day 0 antibody titre; study site; crying when vaccine given (aerosol arm only); presence of respiratory tract symptoms at time of vaccination (aerosol arm only). In addition, random subsets of 80 infants each with OD 0.1-0.2 and OD>0.2 at day 91 will be assessed for PRNT antibody concentrations to determine the relationship between PRNT and Enzygost optical densities/concentrations and validate the use of the cut-off of 0.1 for PRNT testing.

For infants in the day 28 blood sample subset or the day 364 blood sample subset:

- Geometric mean titres to describe evolution of antibody response at days 0, 28, 91, 364;
- Seropositivity at 364 days in infants with antibody titre \geq 120 mIU/ml at day 91.

10 Assessment of Safety

10.1 Primary outcome

Adverse events up to and including day 91 post-vaccination.

10.2 Secondary outcomes

• Frequencies of individual adverse events

For further details of assessment and management of adverse events, please see Section 8.7 and SOPs WHO 1/1, WHO2/1, WHO 3/1.

11 Statistics

11.1 Description of statistical methods

A detailed analysis plan will be finalised prior to locking of the database and commencement of statistical analysis.

11.1.1 Analysis sets

- Primary analysis: per protocol (infants receiving the allocated vaccine and available for follow up at 91 days post-vaccination). For non-inferiority hypothesis, this is the conservative analysis;
- Secondary analysis: intent-to-treat analysis (all infants randomized, analysed in the group to which they were allocated, irrespective of intervention received) of primary and secondary outcomes.

11.1.2 Statistical methods, immunogenicity

• Primary analysis: calculate two-sided 95%CI for the difference in proportion seropositive at day 91.

 Secondary analyses: include calculation of 95% confidence intervals for seropositivity, seroconversion and geometric means as well as multivariable logistic and normal errors regression adjusting for covariates.

11.1.3 Statistical methods, safety

- Primary analysis: proportion (with 95% CI) with any adverse events in aerosol group and in subcutaneous group;
- Secondary analysis: proportions (with 95% CI) of individual adverse events.

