6.2.2 Safety

6.2.2.1 Primary outcome

Adverse events up to and including day 91 post-vaccination;

Adverse events include acute clinical reactogenicity, other adverse events, and serious or unexpected adverse events.

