6.3.1.2 Sequence generation

The allocation sequence will be computer-generated random numbers, in permuted blocks, generated by an independent statistician. The randomization ratio will be 1:1.

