11.2 Sample size

11.2.1 Immunogenicity

Total to be enrolled, 2000. Number available for primary analysis (after loss to follow up), 1600. These numbers are based on the following assumptions:

- Significance 2.5%, one-sided for non-inferiority, 5% two-sided for superiority;
- Non-inferiority margin 5%;
- Power for non-inferiority 90% if true seroconversion is 90% in both arms;
- 20% loss to follow up by day 91.
- Calculate two-sided 95%CI for difference in proportion seropositive at day 91. If lower limit of difference greater than -5% then conclude non-inferiority. If lower limit of difference greater than 0% then conclude superiority.

With 100 children sampled at random from those being followed up, based on a standard deviation of post vaccination titres of 0.43, differences of <1.5 fold in geometric mean titres between aerosol and subcutaneous groups between days 28 and 364 would be able to be detected at a 5% level with 80% power. Smaller differences between days 28 and 91, and 91 and 364 would also be detectable.

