11.2.2 Safety

To estimate proportions with adverse events in aerosol and subcutaneous groups, the sample sizes above give acceptable precision.

Observed proportion	95% confidence intervals		
	N=100	N=800	N=1000
0%	0.00 - 3.6%	-	0.00 - 0.37%
1%	0.02 - 5.44%	0.43 - 1.96%	0.48 - 1.83%
2%	0.24 - 7.04%	1.15 - 3.23%	1.26 - 3.07%
5%	1.64 – 11.28%	3.60 - 6.75%	3.73 - 6.54%

With 1000 infants in each group the precision of estimation of adverse events is:

If no reactions are observed, the upper 95% confidence interval with a sample size of 1000 is 0.37%, or 1 in 270.

With 100 children sampled at random for follow up to 364 days, the precision for estimating the prevalence of rare events is low. If zero events are observed by day 364 the upper 95%CI will be 3.6% (1 in 28).

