11.5.6 Data sharing and analysis

Data will only be accessed by the sub-investigator in charge of data management and statistical analysis. The DSMB will receive quarterly unblinded reports. See SOP VEL 1/1

Outliers, missing values, and inconsistencies will be identified based on the Validation Check Specification document (in SOP VEL 2/1). If inconsistencies arise then the query will be raised at this level. Based on the query responses, corrections will be made in the original ACCESS database. Having completed all the corrections, the data will be exported to SAS software format. Data analysis will be carried out after all enquiries have been done and the database has been locked. Any data which is still missing after enquiries have been made will be dealt with as described below:

• Missing values

For the per-protocol (PP) dataset, missing values will be treated as missing at random. For the intention-to-treat (ITT) dataset, the analysis will also be run with imputed values for the missing values, for the best and worst case scenarios. In the best case scenario, we will assume no adverse events occurred and the individuals are seropositive. In the worst case scenario, we will assume an adverse event occurred and the individuals are seronegative.

• Outliers

For log 10 PRNT values [LPRNT], checks for outliers will be performed prior to the statistical analysis, as part of the data checking. The outliers will also be examined using standardized residuals >3 when looking at log 10 PRNT values [LPRNT].

12 Procedures for reporting any deviations from the original analysis plan

Any change in the planned analysis will be described and documented in the study report including the time (specifically whether prior to or after unblinding occurs) and reason for the change, the procedure used to decide on the change and the nature and content of the data available when the change was made.

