The primary efficacy analysis for safety includes all children vaccinated, according to the route of vaccination that they received and with at least one safety assessment.

In addition, we will summarize explicitly any severe reactions or serious adverse events (SAE) in children vaccinated by the wrong route.

11.5 Timing of Analyses:

The primary efficacy analysis will be conducted after the last enrolled participant completes the day 91 follow up visit.

Every 3 months the data will be analyzed and a report will be made available for the DSMB. This report will focus on safety.

11.6 Method for Handling Missing Data:

For the primary efficacy analysis there is no plan to impute data values for participants who do not complete follow up visits.

For the PP dataset, missing values will be treated as missing at random. However, preliminary analyses such as age, sex, baseline immunogenicity distribution will be studied between the two groups to examine the validity of this assumption.

For the assessment of immunogenicity, missing values (e.g. no blood taken) are treated as if they are missing at random. The OD values for blood samples taken outside the specified time limits will be treated as missing values.

Note that missing values at 91 days post-vaccination and at other time points will be considered for further analyses. The missing information will be handled by best and worst case scenario methods. Where blood specimens are taken outside the recommended time interval, these results will still be used.

11.7 Significance Level:

This is a non-inferiority trial and the confidence interval approach will be used to determine the trial outcome. For additional analyses, such as those adjusting for covariates, we will not use a fixed 'statistical significance' level for reasons described by Sterne and Davey Smith (3). For analyses that require the calculation of p values, we will base our interpretation on examination of the effect size, confidence interval and p value.

11.8 Safety:

We will estimate the proportions (with 95% CI) of AE in each arm according to the definitions of the primary and secondary safety outcomes (Refer section 8.7 in the protocol).

SOP VEL 1/1:	Statistical Analysis Plan	Page 10 of 61
September 11, 2012		

11.9 Covariates to be examined:

Covariates of interest are as follows:

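### The day-91 adverse-event risk is a crude proportion that ignores partial follow-up, so the primary safety estimate is biased low, modestly under the planned loss, and the protocol and SAP differ on its denominator

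*Supplement*

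**What the plan says.** - **Outcome.** The primary safety outcome (protocol 6.2.2.1 and 10.1) is cumulative: "Adverse events up to and including day 91 post-vaccination".
- **Estimator.** Protocol 11.1.3: "Primary analysis: proportion (with 95% CI) with any adverse events in aerosol group and in subcutaneous group". Protocol 12.1.3 and SAP 11.8 repeat the simple proportion with its interval.
- **Denominator, SAP 11.4 (As Treated).** This set is described as follows: "primary efficacy analysis for safety includes all children vaccinated, according to the route of vaccination that they received and with at least one safety assessment".
- **Denominator, protocol 11.1.1.** The general primary set is limited to infants who received the allocated vaccine and were available at day 91. It is justified by the non-inferiority hypothesis. No separate safety set is named.
- **Loss.** The immunogenicity sample size (protocol 11.2.1) assumes "20% loss to follow up by day 91".
- **Missing values.** Protocol 11.5.6 plans two imputed runs on the ITT dataset. One is: "In the best case scenario, we will assume no adverse events occurred and the individuals are seropositive". The other assumes that an event did occur. SAP 11.6 keeps best- and worst-case handling for further analyses.
- **Precision.** Protocol 11.2.2: "If no reactions are observed, the upper 95% confidence interval with a sample size of 1000 is 0.37%, or 1 in 270".

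The documents give no person-time, at-risk denominator or time-to-event method for safety.

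**The concern.** A crude proportion estimates a 91-day risk only if everyone in the denominator is observed for 91 days. Every vaccinated child has the 30-minute observation. If that counts as a safety assessment, the SAP condition excludes almost nobody, and an infant who leaves on day 5 with nothing recorded stays in the denominator as a non-event to day 91. That is the same assumption as the protocol's best case, but here it sits in the main estimate.

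Describing adverse-event frequency by route is a primary objective and supports licensure. The error runs in the reassuring direction. If loss differed between the arms of this open-label trial, the arm with more loss would look safer.

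**Working it through.** **Reproducing the plan's figures.** Enrolment is 2,000 and "The randomization ratio will be 1:1", so 1,000 per arm. With 20% loss, 2,000 × 0.8 = 1,600 ("Number available for primary analysis (after loss to follow up), 1600"), or 800 per arm. The exact upper limit with no events is 1 − 0.025^(1/n). It is 0.368% for n = 1,000, which agrees with the stated 0.37%, and 0.460% (1 in 217) for n = 800. SAP Table 8.2.1 prints 0.46%; the matching cell in protocol 11.2.2 is blank. The other rows for N = 800 and N = 1,000 reproduce except one: 20/1,000 gives 1.23–3.07%, against a printed lower limit of 1.26% in both tables.

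**Relative bias.** An event is missed if the infant was lost before it, so relative bias = average of L(t) over first-event times, where L(t) is cumulative loss. Assume 20% loss spread evenly, L(t) = 0.2 × t/91. Let a share e of first events fall evenly in days 0–14 and the rest evenly in days 14–91:

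bias = e × 0.2 × 7/91 + (1 − e) × 0.2 × 52.5/91 = 0.0154e + 0.1154(1 − e)

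| Share of first events by day 14 | Relative bias | True 5% reported as |
|---|---|---|
| 15% (even over 91 days) | 10.0% | 4.50% |
| 50% | 6.5% | 4.67% |
| 80% | 3.5% | 4.82% |
| 95% | 2.0% | 4.90% |

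If all loss falls after day 28, the range is 0.4–7%. The ceiling of 20% needs every lost infant to leave on day 0 before any event is recorded.

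**Effect on the interval.** Count each window's first events only in infants who reach the visit that closes it. Even loss gives cumulative losses of 3.1, 6.2, 12.3 and 20% at days 14, 28, 56 and 91. With an assumed true risk of 60%:

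- Events spread out (30/40/50/60% by those days): 30 × 0.969 + 10 × 0.938 + 10 × 0.877 + 10 × 0.800 = 55.2%.
- Events early (50/55/58/60%): 50 × 0.969 + 5 × 0.938 + 3 × 0.877 + 2 × 0.800 = 57.4%.

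The table gives exact binomial coverage of the nominal 95% interval, n = 1,000, with the same onset shapes scaled down for the lower risks.

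| Assumed true risk | Coverage, spread out | Coverage, early |
|---|---|---|
| 60% | 14% | 61% |
| 15% | 83% | 92% |
| 5% | 92.5% | 94.9% |

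If all loss falls just before the day-91 visit, the bias at 60% is 10 × 0.2 = 2.0 points (spread out) or 2 × 0.2 = 0.4 points (early).

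**Window tables.** If Table 13.1.1E(2) divides by all vaccinated infants and 20% have no day-91 assessment, a true 10% in days 57–91 becomes 10% × 0.8 = 8.0% (80/1,000, exact CI 6.4–9.9%).

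**Unequal loss.** With 25% loss on aerosol, 15% on subcutaneous and an identical 60% risk, aerosol looks 2.4 points safer (54.0 v 56.4%, spread out) or 1.3 points safer (56.7 v 58.0%, early).

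**Width of the best/worst bracket.** Suppose 40 events are seen in 800 completers and none in the 200 lost. The best case is 40/1,000 = 4.0% and the worst case is (40 + 200)/1,000 = 24.0%.

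**The case against.** Much of the opposing case stands.

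- A reader might infer that every lost infant is counted as event-free. The documents do not support that. Protocol 8.7 schedules nine contact days before day 91 (0, 3, 7, 10, 14, 17, 21, 28, 56), and an event recorded before loss counts. Only infants lost without a recorded event enter as zeros.
- The 20% is an immunogenicity assumption. A missed blood sample is not lost safety follow-up: most adverse-event contacts are home visits, non-attenders are sought at home, and active surveillance and parental reports add information. Safety follow-up may exceed 80%.
- The protocol plans a worst case as well as a best case, so the bias is bracketed. But those runs are assigned to the ITT dataset or to further analyses, and the bracket can be too wide to give a central estimate.
- A reader might also infer that the stated intervals generally miss the true risk. That needs a high risk and early loss. The documents give 5–15% for fever and 5% for rash after subcutaneous vaccination, where the effect is moderate or small. The 60% and the onset curves come from no document.
- The footnote defining the population in Tables 13.1.1 and the safety flow chart are not visible in the text available, so the window-table result is conditional.
- Kaplan-Meier itself assumes non-informative loss.

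The protocol's day-91 set does not resolve the matter. Applied to safety, it would discard events seen in infants who later left.

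**Conclusion.** The point holds in limited form. The two documents differ on the safety denominator, and neither handles partial follow-up in the main estimate. Under the SAP rule, the cumulative proportion is biased low whenever infants are lost before a first event. The relative size is about 2–10% if 20% are lost evenly over 91 days, and less if loss is late or home visits keep safety follow-up above 80%. Under-coverage matters mainly for the any-event outcome if that risk is high; individual events near 5% are little affected. Timing of events, timing of loss and the 60% risk are assumptions. The plan should be changed, but this does not invalidate the safety analysis.

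**What to change.** - In SAP 11.8 and protocol 11.1.3 and 12.1.3, state one safety denominator. Estimate the day-91 risk of any adverse event in each arm by Kaplan-Meier, using first onset, censoring at the last completed adverse-event contact, and giving a log-log 95% interval. Report the crude as-treated proportion alongside, labelled as the lower bound.
- In SAP Tables 13.1.1B(2) to E(2), use as denominator the infants with an adverse-event assessment closing that window, and define it in the footnote.
- Minor: enter 0.46% in the blank 0%, N = 800 cell of protocol 11.2.2, as the SAP already does, and correct the lower limit for 2% at N = 1,000 from 1.26% to 1.23% in both tables.

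The cost is SAP wording and a little programming: onset dates are already in the Table 13.4.1 listing, and the CRFs record the visits. The price is a stated assumption of non-informative loss, which the planned best- and worst-case runs can continue to probe.
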